1.0 Objective

1.1 Primary objectives

To determine the efficacy of talimogene laherparepvec in inflammatory breast cancer or non-inflammatory breast cancer patients with inoperable local recurrence measured by the overall response rate

1.2 Secondary objectives

[figure not shown]
- To determine the efficacy of talimogene laherparepvec in inflammatory breast cancer or non-inflammatory breast cancer patients with inoperable local recurrence measured by the overall disease control rate
- To determine the rate of local overall response and disease control rate, progression-free survival (PFS), and overall survival (OS) in all patients.
- To determine the rate of local overall response and disease control rate, PFS, and OS in patients without distant metastases.
- To determine the rate of local overall response and disease control rate, PFS, and OS in patients with distant metastases.
- To determine the safety of talimogene laherparepvec injection to local disease.

1.3 Correlative studies

- To determine the effect of talimogene laherparepvec on injection sites and distant metastatic sites by evaluating immune function and apoptosis with immune cell surface markers and cytokines. Talimogene laherparepvec induces systemic immune reaction through activation of dendritic cell, and enhance cellular immunity. Cytotoxic T-lymphocyte (CTL) is estimated to offense distant cancer cells via apoptosis mechanism and humoral immunity was not determined to involve in this systemic immunity. However, the activation of dendritic cells may subsequently activate NK-cells and B-cells. Other leukocyte such as neutrophil and monocyte are currently undetermined their function within systemic immune reaction induced by talimogene laherparepvec (Figure 1).
- To assess changes in the following:
 - Serum or plasma levels of interleukin (IL)-2, IL-12, tumor necrosis factor (TNF)-alpha (α), and interferon (IFN)-alpha (α); ([name]'s Lab)
 - Phenotype for T-cell subsets (CD3, CD4, CD8, CD25) and NK-cell subsets (CD16, CD56), which will be determined via multiparameter FACS analysis (percentage and absolute numbers) in peripheral blood at [name] laboratory of MD Anderson.
 - Serum analysis of herpes simplex virus (HSV) type 1 serology with immunoglobulin (Ig)G and IgM (ELISA)
- To assess distant tumor tissue changes by evaluating necrosis and immune cell infiltration (T-/B-/NK-Cell, macrophage, dendritic cell) by immunohistochemistry assay (CD3, CD4, CD8, CD20, CD16, CD56, Granzyme B, cleaved caspase 3, and Ki-67) when distant tumor sample is obtained. If the sample volume is ample, additional immunohistochemistry assays will be performed for CD45RO, TIA-1, FoxP3, CD25, OX-

40, CD57, CD1a, CD208, myeloperoxidase, CD68, COX-2, MHC Class I and MHC Class II in [name] laboratory at MD Anderson.

Figure 1: Systemic immune response expected to be related to talimogene laherparepvec administration

Talimogene laherparepvec induces systemic immune reaction through activation of dendritic cell, and enhance cellular immunity (IL-2, IL-12, TNF- α , IFN- α , CD3, CD4, CD8, CD25, CD45RO, TIA-2, FoxP3, OX40, CD1a). Cytotoxic T-lymphocyte (CTL) is estimated to offend distant cancer cells by apoptosis mechanism (cleaved caspase3) and humoral immunity was not determined to involved this systemic immunity. However, the activation of dendritic cells (CD208, MHC class I and II) may subsequently activate NK-cells (CD16, CD56, Granzyme B, CD57) and B-cells (CD20). Other leukocyte such as neutrophil (myeloperoxidase) and monocyte (CD68) are currently undetermined their function within systemic immune reaction induced by talimogene laherparepvec.

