3.0 Rationale

Local recurrence of breast cancer can result in substantial morbidity and also frequently leads to systemic metastases. Modalities used to treat locally recurrent breast cancer include chemotherapy, hormone therapy, radiation therapy, and surgery. Compared with distant metastases, local recurrence is staged as possible curative status if additional surgery is available, however this opportunity is limited for patients with minor local disease having had conservative

surgery. In addition, survival improvement has not well been demonstrated due to lack of new modality of local treatment.

Current treatment modalities for locally recurrent breast cancer depend on the operability of lesions, disease aggressiveness, previous chemotherapy or radiation therapy, and histologic subtypes; thus, a new modality for treating local disease is needed, since systemic therapy is currently the last resort intervention. Talimogene laherparepvec is immunotherapy with a dual mechanism of generating local tumor lysis and systemic antitumor immune response. In a previous phase I study, talimogene laherparepvec as a single agent was shown to induce tumor necrosis in breast cancer.

The purpose of this study is to determine the local and systemic antitumor efficacy of talimogene laherparepvec in locally recurrent breast cancer patients with or without distant metastases, as evidenced by improved overall response rates. This will be the first study to use biopsy of distant disease to demonstrate whether systemic immune modulation has antitumor efficacy in breast cancer patients. We will also evaluate the antitumor effects of talimogene laherparepvec via comprehensive imaging such as chest x-ray, ultrasound, computed tomography (CT), and positron emission tomography ¹⁶CT as clinically indicated. In addition, we will conduct multiple biological correlative studies to understand the role of immune response activated by talimogene laherparepvec in breast cancer. Patients with initially inoperable local recurrence can be candidates for surgery with curative intent if their tumors become operable.

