Tumor biopsies were stained for a variety of T cells (expressing CD3, CD4, CD8, CD30, and CD68 markers). All biopsies were positive for these cells. However, no obvious patterns emerged and, in the absence of baseline data, it is not possible to conclude that T cell levels were elevated as a result of treatment.

Quantitative PCR also was performed to evaluate the presence of hGM-CSF mRNA in order to measure talimogene laherparepvec –encoded GM-CSF versus endogenous GM-CSF. Of 13 biopsies with partial or extensive tumor necrosis, 11 (84.6%) showed measurable quantities of talimogene laherparepvec encoded GM-CSF mRNA, and the level of mRNA expressed was dose dependent (i.e., more GM-CSF mRNA was expressed after administration of higher doses of talimogene laherparepvec). Additionally, seronegative patients expressed more GM-CSF mRNA than did seropositive patients.

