7.2.12. Breast sonography with axillary assessment if clinically indicated

7.2.13. Ultrasound-guided core biopsy of local recurrence if samples (i.e., paraffin block or 5-10 unstained slides from the local recurrence) are not available. The imaging physician will perform the biopsy if indicated at MD Anderson.

7.2.14. HSV serology: serum HSV type 1 IgG.

7.2.15. Systemic immunity in serum or plasma levels of, IL-2, IL-12, TNF-alpha (α), IFN- alpha (α); and phenotype for T-cell subsets (CD3, CD4, CD8, CD25), and natural killer-cell subsets (CD16, CD56) will be determined via multiparameter fluorescence activated cell sorting (FACS) analysis (percentage and absolute numbers) in [name] laboratory at MD Anderson.

7.2.16. Photography of the local recurrence in the chest wall.

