8.2. Evaluation of distant metastases (before cycle 5)

If a patient has distant metastasis, every effort will be made to obtain tissues from an easily accessible metastatic site. If patient does not have distant metastasis or distant metastasis is not accessible, core biopsy of local lesions will be needed to collect tumor tissue. Every effort will be made to obtain biopsy tissue before cycle 5 for at least 60% of enrolled patients.

A pathologist collaborator will be notified before the biopsy and will handle the resected specimen. Every attempt will be made to identify any tumor change such as necrosis.

Hematoxylin and Eosin staining will be performed with formalin-fixed paraffin-embedded

blocks to determine tumor, and immunohistochemical (IHC) staining will be made for immunity assessment. IHC assays will include CD3, CD4, and CD8 for T-cell immunity assessment, CD20 for B-cell immunity assessment, and CD16, CD56, and Granzyme B for NK cell immunity assessment. Cleaved caspase 3 staining for an apoptosis assay, Ki67 for a proliferation assay, and HSV antigen staining will be performed. If the remaining sample is ample, CD45RO, TIA-1, FoxP3, CD25, OX-40, CD56, CD57, CD1a, CD208, myeloperoxidase, CD68, COX-2, MHC Class I, and MHC Class II will also be assessed in [name] laboratory at MD Anderson.

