8.3 Study Calendar

Evaluation and treatment	Screening	Cycle 1 Day 1	Cycle 2 (D22+/-5 days)	Cycle 5 (D64 +/- 5 days)	Cycle 7 and every 2 cycles	Follow up⁹
Time	Baseline (within 6 weeks)	Prior to talimogene laherparepvec injection				
Eligibility, screening, consent, and registration	X					Patients will be monitored for 1 year after removal from the study or until death, whichever occurs first.
Medical history	X					
Staging with tumor measurements	X					
Photography of chest wall	X ¹		X	X	X	
Biopsy of local recurrence [HE, IHC]	X ⁸			X ⁸		
Biopsy of easily accessible distant metastasis [HE, IHC]				X ⁸		
Correlative immune study	X			X ⁷		
Physical examinations, vital signs	X	X ²	X	X	X	
ECOG PS	X	X ²	X	X	X	
Hematology assessment and Biochemical profiles ^{3,5}	X	X ²	X	X	X	
Tumor markers (CA27.29) ¹¹ , IgG (baseline only)	X			X	X ¹¹	
Chest X-ray; Breast sonography ¹³	X					
Pregnancy test if applicable ¹⁰	X					
PET-CT or CT scan of bone/abdomen/chest as clinically indicated	X			X	X ⁴	
Disease assessment ¹²				X	X	

Adverse events ⁵	X	X	X	X	X	
Talimogene Laherparepvec injection ⁶		X	X	X	X	

1. Within 1 week prior to treatment
2. No need to repeat if within 7 days from baseline
3. Hematology include CBC, differential count and platelet count; and biochemical profiles SMA include Na, K, BUN, creatinine, Mg, calcium, AST, ALT, LDH, total bilirubin
4. Repeat every 4 cycles as clinical indicated
5. Before each cycle. Reporting exposure to talimogene laherparepvec and should be collected for the duration of the study and safety f/u
6. Starting cycle 2, Talimogene Laherparepvec injection will be given every 2 weeks until disease progression
7. Correlative immune study will be repeated before cycle 5 and at the end of study if available.
8. Core biopsy of local recurrence at baseline if samples (i.e., paraffin block or 5-10 unstained slides) from the local recurrence are not available. Core biopsy of either distant metastasis or local recurrent lesions before cycle 5 based on patient status.
9. a. Safety Follow-Up: should be conducted approximately 30 days after the last dose of trial treatment or before the initiation of a new anti-cancer treatment, whichever comes first. Safety Follow-Up Visit can be done in the clinic, or by phone if patient is not willing to come to the clinic for follow up.
- b. Unexpected AEs: Patients removed from study for unexpected adverse events will be monitored until AE is resolved or stabilized.

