Secondary objectives includes determining the overall disease control rate, local overall response rate and disease control rate, PFS, and OS in all patients; the local overall response rate and disease control rate, PFS, and OS in patients without distant metastases; and the local overall response rate and disease control rate, PFS, and OS in patients with distant metastases for defining the local efficacy of talimogene laherparepvec injection among breast cancer patients with inoperable local recurrence after surgery. In addition, this includes safety and tolerability of talimogene laherparepvec in these patients. The definition of PFS is time from treatment initiation until disease progression or death and this progression needs to be confirmed after the end of cycle 10. For example, patients who showed progress at 2 months but responded as PR at 5 months, we determine this as PR. In contrast, patients who showed progress at 2 months and was confirmed PD at 5 months, we determine this as PD at 2 months. The definition of OS is time from treatment initiation until any cause of death.

Analysis plan:

By the end of the study, the overall response rate will be estimated with 95% confidence intervals for all evaluable patients and for patients with or without distant metastasis, separately. PFS and OS from registration will also be estimated using Kaplan-Meier method with 95% confidence intervals.

Biomarker endpoints will be measured in tissue and in surrogate blood or plasma before and after the treatment. Correlation between biomarkers from various markers and between tissue and blood/plasma will be assessed by Pearson or Spearman rank correlation coefficients for

continuous biomarkers and by chi-square or Fisher's exact test for discrete covariates. The associations between markers or change in the level of markers and overall response status will first be assessed graphically and then tested using a t-test/analysis of variance or Wilcoxon rank sum test/Kruskal-Wallis test, when appropriate. Repeated measures analysis including mixed effects modeling will be performed to analyze biomarkers change over time. We may also evaluate the association between the changes in the level of marker and the overall response status.

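### Change in distant tumour tissue is an exploratory objective, but no distant tissue is scheduled before treatment, so treatment and site cannot be separated

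*Combined protocol and SAP*

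**What the plan says.** **Objective.** Section 1.3 lists "To assess distant tumor tissue changes by evaluating necrosis and immune cell infiltration" by immunohistochemistry, subject to the condition "when distant tumor sample is obtained". Section 3.0 gives distant biopsy a prominent place: "This will be the first study to use biopsy of distant disease to demonstrate whether systemic immune modulation has antitumor efficacy".

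**Baseline tissue.** Section 7.2.13 asks for "Ultrasound-guided core biopsy of local recurrence if samples (i.e., paraffin block or 5-10 unstained slides from the local recurrence) are not available". Footnote 8 to the 8.3 calendar has the same rule. Neither mentions tissue from a metastasis, fresh or archival.

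**On-treatment tissue.** Footnote 8 continues: "Core biopsy of either distant metastasis or local recurrent lesions before cycle 5 based on patient status". Section 8.2 prefers a metastasis that can be reached easily. If there is none, or it cannot be reached, "core biopsy of local lesions will be needed to collect tumor tissue". The target is tissue from at least 60% of enrolled patients, distant and local combined.

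**Analysis.** Section 13.1 states: "Biomarker endpoints will be measured in tissue and in surrogate blood or plasma before and after the treatment". It plans mixed models for change over time and tests of marker change against overall response. It has no term for site or injection status and no restriction to same-site pairs.

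**Which local lesion.** Section 6.1, item 3, keeps the lowest-priority lesion uninjected until biopsy, but only in patients without distant metastases. The Figure 4 legend refers to distant disease or a non-injected local site, and marks that biopsy as optional.

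**The concern.** A change needs a before and an after at the same place. The distant objective has only an after. If distant cycle 5 tissue is set against the local baseline, a difference in CD8 cells, granzyme B, cleaved caspase 3 or necrosis could reflect how a node or other metastasis differs from chest wall, not what the drug did.

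The protocol accepts the underlying principle. Of the phase 1 biopsies, section 4.4.3 says that "in the absence of baseline data, it is not possible to conclude that T cell levels were elevated as a result of treatment". The present schedule leaves the same gap for distant tissue.

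The local fallback raises a related issue. The first bullet of 1.3 separates effects at injection sites from effects at distant sites. If injected and uninjected local specimens are pooled, direct lysis and any systemic immune effect can no longer be told apart.

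What is at stake is the interpretation of the trial's tissue evidence for a systemic effect, and the value of a biopsy taken to obtain it.

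**Working it through.** There is no stated figure to reproduce. The check sets the schedule against the analysis.

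**1. Which tissue exists, by site and time**

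| Site | Before treatment | Before cycle 5 |
|---|---|---|
| Local | Yes (7.2.13; footnote 8) | Yes, if no metastasis can be sampled (8.2; footnote 8) |
| Distant | None scheduled or requested | Yes, if present and accessible (8.2; footnote 8) |

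The calendar's distant-biopsy row carries one mark and the local row two. Column positions are uncertain in the extracted table, but 8.2 and footnote 8 give the same reading in words. Scheduled same-site distant pairs: 0.

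**2. What a cross-site difference measures**

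For a patient with a distant specimen:

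(distant, cycle 5) − (local, baseline) = [(distant, cycle 5) − (distant, baseline)] + [(distant, baseline) − (local, baseline)] = treatment effect + site difference.

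The distant baseline value is never observed, so the two terms cannot be separated.

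**3. Whether a site term would repair it**

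It would not. With three of four cells filled, a model with time and site as main effects takes its time effect from the local pairs and assumes that the same change holds at distant sites. Whether distant tissue changes is the question being asked, and the site-by-time interaction that would answer it cannot be estimated.

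**4. Size, by illustration only**

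The documents give neither a site difference nor the number of distant specimens, so both are assumed here. Sixty per cent of 36 is 21.6, about 22 patients; the rows below take 22 (all distant), 11 and 6 pairs. With zero treatment effect and a site difference of d standard deviations of the paired differences, the rejection rate of a two-sided 5% paired t-test comes from the noncentral t distribution with n − 1 degrees of freedom and noncentrality d√n:

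| Pairs | d = 0.25 | d = 0.5 | d = 0.8 | d = 1.0 |
|---|---|---|---|---|
| 6 | 8% | 17% | 36% | 51% |
| 11 | 12% | 32% | 67% | 85% |
| 22 | 20% | 61% | 95% | 99% |

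The paired t-test stands in for the planned change models. If cross-site pairs were pooled with local pairs, the bias in the mean change would shrink in proportion to the cross-site share but would not vanish.

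**5. Local fallback, side by side**

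Section 6.1 protects an uninjected lesion only when there are no distant metastases. Section 8.2 sends patients whose metastases cannot be reached to local biopsy as well, and for them 6.1 reserves nothing. Section 5.1.10 admits patients with a single injectable lesion, for whom an uninjected local sample may not exist. The Figure 4 legend points to a non-injected site; 8.2 does not say.

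**The case against.** The strongest reply is that the faulty comparison is nowhere written. Section 13.1 is generic: it covers tissue and blood together, and the blood markers listed in 7.2.15 do have baseline and on-treatment samples (8.1.8). Tissue-blood correlations need no before/after pair. This stands. A reader might infer that the plan commits to comparing local baseline with distant cycle 5 tissue; it does not. What remains is that no other distant change can be computed, and nothing in the plan rules this one out.

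Three other stronger readings go too far:

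- Section 3.0 might be read as promising that biopsy will show systemic efficacy. The sentence says whether, so it poses a question.
- Section 4.4.3 might be read as evidence of site confounding in phase 1. It reports only that baseline data were lacking, and also that no clear pattern appeared.
- Injected and uninjected local tissue might be said to be mixed. Section 6.1, item 3, and the Figure 4 legend partly prevent this; pooling is possible, not established. Figure 4 itself is not shown, so its biopsy markers cannot be checked. HSV antigen staining (8.2) and photographs with an injection marker (9.0) would help to classify specimens, though no specimen-type record or separate analysis is stated.

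Nor can the number of affected patients be given, because the distant/local split is not stated. Finally, the objective is correlative and conditional. No tissue marker is a primary or secondary endpoint (13.2, 13.3) or enters a stopping rule. That limits the importance of the point but does not remove it.

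**Conclusion.** The point holds in limited form. Change in distant tumour tissue cannot be estimated within a patient under this schedule, because there are zero scheduled same-site distant pairs. Any tissue change computed for a patient with a distant specimen would combine treatment and site, and 13.1 neither excludes such a difference nor has the data to correct it.

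The zero rests on the documents alone. The false-positive rates rest on assumed site differences and pair counts and show only that the effect need not be small. Patients with local tissue at both times are free of the local-versus-distant problem, though injection status may still differ, and they do not inform the distant objective.

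The primary endpoint, the secondary endpoints and the blood markers with a baseline are unaffected. The point is worth correcting because it changes what the tissue work can conclude, but it concerns an exploratory objective only.

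**What to change.** 1. In 13.1, restrict tissue-change analyses, including change against response, to same-site pairs, and exclude differences between local baseline and distant cycle 5 tissue.
2. Record each cycle 5 specimen as distant, local uninjected or local injected at the time of biopsy, and analyse the three groups separately.
3. In 1.3 and 3.0, describe unpaired distant tissue as on-treatment findings, not as change.
4. Optionally, in 7.2.13 and footnote 8, request existing archival tissue from the metastatic site, with its date and any intervening therapy. Such tissue may predate other treatment, so a pair built on it would still mix the study drug with time and earlier therapy and should be reported with that caution.
5. Reconcile 6.1, 8.2 and the Figure 4 legend on which local lesion is meant, including for patients whose metastases cannot be reached, and on whether the biopsy is optional.

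The cost is protocol wording, one specimen field and, if item 4 is taken up, archival requests. No extra biopsy is needed. The price is fewer patients in the tissue-change analysis and a more modest claim about distant tissue.

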2.0 Background

2.1 Overview of breast cancer local recurrence

2.1.1 Breast cancer local recurrence

Recurrent breast cancer is commonly incurable, and multimodality treatment options have been developed. Following mastectomy or breast-conserving surgery, the 10-year incidence of locoregional recurrence (LRR) is about 13%¹. The local recurrence rate of inflammatory breast cancer (IBC) is higher than that of locally advanced non-infiltrating breast cancer². In particular, breast cancer patients with LRR have been found to have 5-year disease-free survival (DFS) rates of 13%-37% and OS rates of 21%-50%³⁻⁵. Moreover, the outcome is poorer after LRR than after local disease only⁶, and concomitant distant metastases carry an even more dismal outcome. In this protocol, we propose a new treatment modality to increase the control rate of measurable and non-measurable disease and to prolong outcomes.

